#### **HYPOTHESIS**

1. ART intensification with raltegravir leads to increases in gut bacterial richness, could possibly affect its composition and/or function.
2. The gut microbiome structure and composition correlates with markers of inflammation, coagulation, enterocyte damage and T-cell activation, maturation and immune senescence.

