#### **4 TRIAL OBJECTIVE AND PURPOSE**

##### **4.1 PRIMARY OBJECTIVE**

To evaluate the ability of raltegravir intensification to increase gut microbiome richness and modify the gut microbiome composition of people living with HIV receiving stable ART.

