### 5.3 ENDPOINTS

#### 5.3.1 Primary endpoint(s)

- Increase in bacterial richness (observed species) at week 48, relative to baseline (week 0).

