#### 5.3.2 Secondary endpoints

- Longitudinal changes in:
  - Gut bacterial composition
  - Gut bacterial function
  - Other estimators of richness and diversity: Chao1, ACE, Shannon, 1/Simpson.
- Association of the gut microbiome composition and richness with:
  - Inflammation: IL-6, IP-10

- Coagulation: D-Dimer
- Enterocyte damage: Intestinal Fatty Acid Binding Protein (I-FABP)
- Bacterial translocation and monocyte activation: LPS-binding protein (LBP), soluble CD14.
- Maturation, activation, exhaustion and immune senescence in CD4+ and CD8+ T-cells: CD3+, CD4+, CD8+, CD45RA, CCR7, CD28, CD27, HLA-DR, CD38, PD-1, CD57.
- CD4 and CD8+ counts
- CD4+/CD8+ ratio
- In case of changes in the microbiome, the quantification of viral reservoir will be done in PBMCs.

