### 10.1 STATISCAL ANALYSIS

- Taxonomic and functional diversity within (alpha-diversity) and between samples (beta-diversity) will be determined. Rarefaction curves will be generated to evaluate sampling efficiency. Diversity measures, reflecting the richness of the microbiome in terms of number of species and abundance of each species will be calculated. This will enable comparisons between groups and timepoints. Ordination methods including principal component analysis and phylum abundance within individuals will be used to check for significant differences between groups. Bacterial abundance and functional profiles will be analyzed with LEFSe. Univariate correlations involving >2 groups will be done applying ANOVA plus Tukey-Kramer post-hoc tests and Benjamini-Hochberg correction; 2-group comparisons will be performed with the Welch's t-test. The relationship between the microbiome and markers of immune activation, inflammation, tissue damage and bacterial translocation will require the application of nonlinear Kernel regression methods.
- Subjects requiring antibiotics for their clinical management during follow-up will not be excluded from the analyses, but the type, duration and reasons for antibiotic intake will be recorded and taken into account in association analyses. Results in HIV-1-infected subjects will be compared to the gut microbiome profiles of healthy HIV-1-negative individuals previously reported by the EU FP7-funded MetaHIT consortium. We will also use microbial ecology theory to describe ecological networks between microbes and between them and the host (degree distribution, clustering coefficient, distance, centrality, community structure, connectivity index, etc.).

*For extensive examples of microbiome analyses available and performed previously by our group at irsiCaixa, please see: Noguera-Julian, M. et al. Gut microbiota linked to sexual preference and HIV infection. EBioMedicine (2016) <http://dx.doi.org/10.1016/j.ebiom.2016.01.032>.*

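### Section 10.1 states no multiplicity correction for the two-arm tests and names no global between-arm test of microbiome composition

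*Combined protocol and SAP*

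**What the plan says.** Section 10.1 is the only place that names statistical tests or a multiplicity correction.

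- **Correction.** Benjamini-Hochberg appears once, in the clause on univariate analyses of more than two groups. Two-group comparisons follow after a semicolon, with no adjustment: "Tukey-Kramer post-hoc tests and Benjamini-Hochberg correction; 2-group comparisons will be performed with the Welch's t-test".
- **Taxa and predicted functions.** "Bacterial abundance and functional profiles will be analyzed with LEFSe". No significance level, effect-size cut-off or correction is given.
- **Composition as a whole.** "Ordination methods including principal component analysis and phylum abundance within individuals will be used to check for significant differences between groups". Also: "Taxonomic and functional diversity within (alpha-diversity) and between samples (beta-diversity) will be determined". No distance measure and no hypothesis test is attached to either sentence.

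The questions these methods must answer are set elsewhere. The primary objective (4.1) is to learn whether intensification can "increase gut microbiome richness and modify the gut microbiome composition". Hypothesis 1 reads: "ART intensification with raltegravir leads to increases in gut bacterial richness, could possibly affect its composition and/or function". The single primary endpoint (5.3.1) is richness, measured as observed species, at week 48 against baseline. Composition, function and four further diversity indices are secondary endpoints (5.3.2), introduced as "Longitudinal changes in".

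Section 5.1 gives two arms; 10.2 gives 40 and 20 patients and calls the study a pilot and exploratory. Sections 5.3.2, 8.1.2 and 8.4 make viral-reservoir quantification conditional on the microbiome having changed, without saying how that is judged.

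**The concern.** In a two-arm trial, each raltegravir-placebo contrast at a visit is a two-group comparison. The plan therefore states a correction where the randomized comparison does not fall and none where it does. Microbiome data offer many features to test, so chance findings among taxa or functions are to be expected if nothing controls them.

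Composition has the opposite problem: there is no single test of it. Principal component analysis displays the data; it does not produce a p-value. A reader of the final report could meet a list of individual taxa and an ordination plot, but no one answer to whether raltegravir modified composition, although the primary objective asks this. The decision to quantify the viral reservoir depends on the same undefined judgement.

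**Working it through.** The plan gives no significance level, false discovery rate or number of features, so it has no figure to reproduce. Its one piece of arithmetic, 40 + 20 = 60 at 2:1, is consistent.

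**1. What each stated method supplies for the between-arm question**

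| Target | Method in 10.1 | Correction stated | Single p-value |
|---|---|---|---|
| More than two groups | ANOVA, Tukey-Kramer | Benjamini-Hochberg | not applicable |
| Two groups | Welch's t-test | none | one per variable |
| Taxa, predicted functions | LEFSe | none | none |
| Overall composition | ordination, phylum abundance | none | none named |

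**2. Size of the missing correction, on a family the plan lists**

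Inputs: Chao1, ACE, Shannon and 1/Simpson (5.3.2), so k = 4; 40 against 20 (10.2); Welch's test (10.1). Assumed: 5% two-sided, each index compared once, no effect.

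If the tests were independent, the chance of at least one false positive is 1 - 0.95^4 = 0.185. The indices are related, so correlation was varied by simulation (equicorrelated normal data, 40,000 runs):

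| Correlation | Uncorrected | Benjamini-Hochberg, q = 0.05 |
|---|---|---|
| 0 | 18.8% | 5.1% |
| 0.5 | 15.5% | 4.6% |
| 0.8 | 11.5% | 3.6% |
| 0.9 | 9.6% | 3.6% |

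Repeat runs gave 15.5% to 15.8%, 11.2% to 11.9% and 9.0% to 9.8% for the last three uncorrected rows.

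**3. The reservoir condition, if limited to two named 5% tests** (primary richness test, global composition test)

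Independent tests: 1 - 0.95^2 = 0.0975. Under any dependence: at most 0.05 + 0.05 = 0.10.

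**4. Whether a global test is workable at 40 against 20**

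Simulated PERMANOVA on Bray-Curtis distances, with the first two baseline principal-coordinate axes and the strata as covariates, and labels permuted within strata (499 permutations). Assumed: 40 genera, logistic-normal abundances, between-genus SD 1.5, subject SD 1, baseline to week-48 correlation 0.6, strata effect SD 0.3.

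- Rejection under no effect (2,000 runs): 5.0% with two strata, 4.7% with four. Repeat runs gave 4.4% to 5.7%, apart from one set of 1,000 at 7.1%, where a fresh 4,000 gave 5.5%. I read the 7.1% as chance, because permutation within strata is valid by construction when subjects in a stratum are exchangeable.
- Power with two strata (1,000 runs):

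| Genera shifted | 0.4 SD | 0.6 SD | 0.8 SD |
|---|---|---|---|
| 10 of 40 | 26% | 55% | 84% |
| 20 of 40 | 54% | 89% | 99% |

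- Sensitivity to spread (Euclidean distances, 30 dimensions, equal centroids): with the smaller arm's SD multiplied by 1.2 or 1.3, the test rejects in 13.5% or 17.9% of runs. With the larger arm's SD multiplied by 1.3, it rejects in 1.0%. A positive result can therefore reflect spread as well as location.

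The results in step 4 test the proposed remedy; they do not measure the gap in the plan.

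**The case against.** The strongest reply is that this is a declared pilot with one primary endpoint, which needs no feature-level correction, and that composition is only secondary as an endpoint. That stands, and it limits the weight of the point. It does not explain why correction is stated for more than two groups and left out for the randomized contrast. The authors may have meant Benjamini-Hochberg to apply throughout, but the text does not say so. The earlier publication cited in 10.1 is offered as a source of examples and pre-specifies nothing.

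The four-index illustration is also open to challenge. The correlations are assumed, and the excess shrinks as they rise (7.4% at 0.97). One comparison per index ignores weeks 12 and 24. If other scalar parameters are also compared between arms, the family is larger. It shows scale only.

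Three stronger readings are tempting, and the documents do not support them:

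- *That adding a global test later must be a deviation under 10.3.* The ordination list in 10.1 is open-ended, so a test attached to an ordination could be seen as carrying out that sentence, and 1.3 provides for protocol modifications.
- *That phyla would be tested one at a time by Welch's test.* Section 10.1 sends bacterial abundance to LEFSe and does not say which test applies to phylum abundance.
- *That the plan would yield a calculable number of false taxa.* At 5%, 50 to 200 raw tests give 0.05 × 50 = 2.5 to 0.05 × 200 = 10 expected false positives. But the feature count is not in the documents and LEFSe was not modelled, so this does not describe the plan.

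**Conclusion.** The point holds as a should-fix improvement to the analysis plan. As written, the two-arm methods carry no stated multiplicity correction, and no global between-arm test of composition is named although composition is in the primary objective. For the four secondary diversity indices, the chance of at least one false positive under no effect is about 10% to 16% at assumed correlations of 0.9 to 0.5, against about 4% to 5% with Benjamini-Hochberg; both rest on an assumed 5% level and one comparison per index. Error across many uncorrected taxon tests would be larger, by an amount that cannot be computed from the documents.

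A reader might infer that the trial's main conclusion is at risk. It is not: the primary richness endpoint is unaffected and the plan states no error rate that could be broken.

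**What to change.** Amend 10.1 before unblinding:

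1. **Correction.** Apply Benjamini-Hochberg at q = 0.05 to two-arm feature-level tests within named families: taxa per rank, predicted functions, and secondary diversity indices. Report the adjusted p-values alongside LEFSe.
2. **Global test.** Pre-specify one between-arm test of composition: PERMANOVA on genus-level Bray-Curtis distances at week 48, or another distance and rank named before unblinding. Use the first two baseline principal-coordinate axes and the strata as covariates, and permute arm labels within the randomization strata actually used. First reconcile 5.4.2, which names ART type and CD4 nadir, with 5.4.1, where only ART type is passed to the CRO with eligibility. Keep weeks 12 and 24 as secondary analyses and principal component analysis as a display. Report a dispersion test; if dispersion is unequal, describe a positive result as a difference in location and/or spread.
3. **Use of results.** Treat taxon-level findings as supportive. Define the microbiome change that leads to reservoir quantification (5.3.2, 8.1.2, 8.4) as a positive primary richness test or a positive global test. State that this condition can be met with up to 10% probability under no effect and can respond to a difference in spread.

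The cost is plan wording and a few lines of R, with no new data. The downside is that fewer individual taxa will be called significant, and at 40 against 20 the global test has low power for small shifts.

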### 5.2 DESCRIPTION OF THE DESIGN

The trial was conducted in a sample of 60 chronically HIV-1-infected adults patients on a stable 3-drug ART with PI/r/c or NRTI/NNRTI and HIV-1 RNA suppression <50 copies/mL, will be randomized 2:1 to intensify their current ART with RAL 1200 mg QD (Intensification arm, n=40) vs. placebo (placebo arm, n=20).

Subjects will be followed prospectively during 48 weeks.

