### 5.4.2 Stratification

Randomization will be stratified by type of ART (PI/r/c or NRTI/NNRTI-based) and CD4 nadir (> 300 or < 300) at screening. In this way, the distribution of these parameters between the study groups will be balanced.

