### **7.3.4 Replacement of patients**

Patients withdrawn by protocol deviation will be replaced by new patients until the expected number of patients. Patients withdrawn by other reasons will not be replaced.

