### 10.2 SAMPLE SIZE DESCRIPTION

This is a pilot exploratory study with no formal sample size calculation. This is, in fact, the first study addressing the effects of antiretroviral therapy intensification on the human gut microbiome. A total of 60 patients will be included in this trial during an inclusion period of 36 weeks. 40 patients in the intensification arm (raltegravir 1200 mg) and 20 patients in placebo arm.

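### Section 10.1 ties no test, scale or covariates to the primary week-48 richness endpoint; the only listed method that fits, an unadjusted Welch's t-test, is valid but generally less efficient than a baseline-adjusted model

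*Combined protocol and SAP*

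**What the plan says.** Section 5.3.1 gives a single primary endpoint: "Increase in bacterial richness (observed species) at week 48, relative to baseline (week 0". It names no between-arm contrast, model or test.

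Section 10.1 introduces the diversity measures, richness included, and adds only: "This will enable comparisons between groups and timepoints". The methods that follow have other stated uses. One is reserved for more than two groups: "Univariate correlations involving >2 groups will be done applying ANOVA plus Tukey-Kramer post-hoc tests and Benjamini-Hochberg correction". LEFSe is for abundance and functional profiles, ordination is for group differences in composition, and kernel regression is for relationships with immune and inflammatory markers. For two groups the plan says "2-group comparisons will be performed with the Welch's t-test". It does not say whether the outcome is change or the week-48 value, and it mentions no covariate.

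On design, Section 5.4.2 states: "Randomization will be stratified by type of ART (PI/r/c or NRTI/NNRTI-based) and CD4 nadir (> 300 or < 300) at screening". Section 10 uses neither factor. Sections 5.2 and 10.2 put 40 patients on raltegravir and 20 on placebo, and Section 10.2 adds: "This is a pilot exploratory study with no formal sample size calculation".

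**The concern.** A two-arm randomised trial with one declared primary endpoint should say how that endpoint will be compared between arms. Here the reader must infer it, and two readings of the same listed test are open: Welch on change from baseline, or Welch on week-48 values. Their precision differs, and which is better depends on a correlation that the documents do not give. Nothing stops the choice being made after the data are seen. Section 10.3 requires deviations from the plan to be justified, but that has little force where no primary analysis is fixed.

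Neither reading adjusts for baseline richness, which every participant will have. With 20 placebo patients and no sample size calculation, the precision of this one contrast largely decides what the trial can say.

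**Working it through.** **Plan's own figure.** There is no power calculation to reproduce. The stated total agrees with its parts: 40 + 20 = 60, which is 2:1.

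**Inputs from the documents.** Arm sizes 40 and 20 (Section 10.2); 2:1 allocation (Section 5.4.1); a 2 x 2 stratification (Section 5.4.2).

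**Assumptions, none in the documents.** SD of 1 at both visits; baseline-to-week-48 correlation rho from 0.3 to 0.9; effect 0.6 SD; two-sided 5%; equal variances; complete data; strata not prognostic.

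**Large-sample variances per patient.**
- Change: 2(1 - rho).
- Week-48 value: 1.
- Baseline-adjusted: 1 - rho².

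The ratio of change to adjusted is therefore 2/(1 + rho), and of week-48 value to adjusted 1/(1 - rho²). At rho 0.5 these are 2/1.5 = 1.33 and 1/0.75 = 1.33. Change is the noisier scale below 0.5, and the week-48 value is the noisier above it.

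**Standard errors.** The common factor is sqrt(1/40 + 1/20) = sqrt(0.075) = 0.274. At rho 0.3 the standard error is 0.274 x sqrt(1.4) = 0.324 for change, 0.274 for the week-48 value and 0.274 x sqrt(0.91) = 0.261 adjusted.

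**Simulation at 40/20.** The adjusted model has arm, baseline and two strata terms (55 residual df) with HC3 (heteroscedasticity-consistent) standard errors. Power for Welch on change and for the adjusted model comes from two sets of 20,000 runs per rho.

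| rho | Variance ratio, change / adjusted | Variance ratio, week-48 / adjusted | Power, Welch on change | Power, Welch on week-48 | Power, adjusted HC3 |
|---|---|---|---|---|---|
| 0.3 | 1.54 | 1.10 | 44% | 55–58% | 57% |
| 0.5 | 1.33 | 1.33 | 57% | 55–58% | 66% |
| 0.7 | 1.18 | 1.96 | 79% | 55–58% | 82% |
| 0.8 | 1.11 | 2.78 | 92% | 55–58% | 93% |
| 0.9 | 1.05 | 5.26 | 99.7% | 55–58% | 99.7% |

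**Expected 95% CI half-width, in SD, at rho 0.3/0.5/0.7/0.8/0.9.**
- Welch on change: 0.652/0.551/0.426/0.349/0.246.
- Adjusted HC3: 0.551/0.499/0.412/0.347/0.252.
- Relative to Welch on change: 0.551/0.652 = 0.85 (15% narrower), 0.499/0.551 = 0.91 (9%), 0.412/0.426 = 0.97 (3%), 0.347/0.349 = 0.99 (1%), 0.252/0.246 = 1.02 (2% wider).
- Welch on week-48 values: about 0.55 at every rho, because the week-48 SD of 1 equals the SD of change at rho 0.5. The adjusted model then gains nothing at rho 0.3 (0.551), 9% at 0.5 and 25% at 0.7 (0.412/0.551 = 0.75).

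**Validity.** Null rejection over the five correlations was 4.8 to 5.1% for Welch on change and 4.0 to 4.4% for HC3. With the placebo residual SD 1.5 times that of raltegravir (rho 0.5), it was 8.4% for ordinary model-based ANCOVA, 4.5% for HC3 and 4.9% for Welch; power at 0.6 SD was 41.5% for HC3 and 38.0% for Welch on change.

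**Fewer patients.** If an assumed 20% lacked a week-48 sample at random (32/16), power would be about 36/47/69/85/99% for Welch on change and 46/54/72/86/99% for HC3: the same pattern at a lower level.

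**Strata.** If they act only through baseline richness (assumed 30% of its variance, rho 0.5), the model that includes them keeps the same 66% power against 57% for Welch on change, so they add nothing beyond baseline.

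**The case against.** The strongest reply is that Welch's test is valid, the trial calls itself a pilot, and the size of any gain depends on a correlation nobody has stated. All of that stands, and it makes this a recommended improvement rather than the repair of an error. It does not supply the missing specification: the same protocol describes a randomised Phase III trial (Section 5.1) and names a primary endpoint.

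A reader might infer more than the documents support in four ways:
- **That the plan specifies Welch on change.** The endpoint wording suggests it, but Section 10.1 gives no scale. On the week-48 reading the loss falls at high correlation instead of low.
- **That the planned test is biased or inflates error.** It does neither.
- **That leaving out the strata costs precision.** This would follow only if they predict week-48 richness beyond baseline, and the documents do not say so. If they did, unadjusted Welch would be conservative.
- **That most withdrawals go unreplaced.** Section 7.3.4 replaces withdrawals for protocol deviation and says of the rest: "Patients withdrawn by other reasons will not be replaced". No shares by reason are given.

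It is also fair that the model proposed here is not the only reasonable one. Stool is collected at weeks 12 and 24 as well (Section 8.5), and a longitudinal model could use it. How to handle missing week-48 stool is a separate question, not settled here.

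**Conclusion.** The point holds as a gap in pre-specification with a cheap and better alternative. No test, scale or covariates are tied to the primary endpoint, and the one listed test that fits is generally less efficient, on either scale, than a baseline-adjusted model.

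At the assumed 0.6 SD effect, the gain over Welch on change is about 13 points of power at rho 0.3, 9 at 0.5, 3 at 0.7, 1 at 0.8 and none at 0.9. The gain over Welch on week-48 values is near nil at 0.3, about 9 points at 0.5 and about 25 at 0.7. The adjusted model matches or beats both readings to within about one point of power at every correlation examined, so the analyst need not guess the correlation. The actual gain is unknown because that correlation is unknown. The figures also rest on normal data, equal variances and complete week-48 samples, except where stated otherwise.

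**What to change.** State in Sections 5.3.1 and 10.1 that the single primary contrast is the raltegravir-minus-placebo difference in week-48 observed species, with its 95% CI, from a linear model with arm and baseline observed species. Use HC3 standard errors, which keep Welch's protection against unequal variances at 2:1 allocation.

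Include ART type and CD4 nadir in the model because randomisation is stratified by them; no precision gain is claimed. Section 5.4.1 has the investigator phone the CRO with eligibility and ART type only, so confirm that the CD4-nadir stratum is recorded at randomisation. If it is not, take it from the nadir collected under Section 8.3.

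**Cost.** The change is to wording, plus that one confirmation; no sample or visit is added. The downsides are:
- Three degrees of freedom are spent.
- HC3 is slightly conservative (null rejection about 4 to 4.5%).
- HC3 costs about 3 to 4 points of power against model-based standard errors at rho 0.3 to 0.5 (57% against 61%, and 66% against 69%).
- At high correlation there is no gain over Welch on change, and at 0.9 the interval is about 2% wider.

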### 10.2 SAMPLE SIZE DESCRIPTION

This is a pilot exploratory study with no formal sample size calculation. This is, in fact, the first study addressing the effects of antiretroviral therapy intensification on the human gut microbiome. A total of 60 patients will be included in this trial during an inclusion period of 36 weeks. 40 patients in the intensification arm (raltegravir 1200 mg) and 20 patients in placebo arm.

